based on a wide range of tests (thigh girth, strength, functional testing, arthrometer evaluation, Lysholm knee scores and EMG) and 6-12 months (Arciero, Scoville et al. 1996). In previous experiments and in our proposed experiments, the thigh cuffs are inflated for only 2-3 minutes. This brief period of ischemia is nearly 30 times less than what has been previously studied in the surgical literature. Given the safety of prolonged thigh cuff inflation, the brief periods of arterial occlusion used in this study are expected to be safe and well tolerated.

The tourniquet system that will be used in this study has been approved by the FDA as a Class-I medical devices, indicating that they present minimal harm to the user and do not present a reasonable source of injury through normal use (Noordin, McEwen et al. 2009). Development in tourniquet systems over the past 30 years make use much safer, including increased cuff width, micro-computer monitoring systems, auto-shut off in event of power failure, battery backup, and audio-visual alarms. Increased cuff width results in lower required tourniquet pressure to stop blood flow (McEwen, Kelly et al. 2002) and should further improve tolerability of cuff inflation.

CHARACTERISTICS OF THE STUDY POPULATION

1. Target Population

Healthy adult volunteers with no history of prior brain ischemia.

2. Accrual

20 subjects provides 90% power to detect a moderate correlation (rho=0.6), with alpha=0.05, based on a single sided test of correlation using Pearson's correlation coefficient. Because of a combination of technical and individual factors, it may be that not all enrolled subjects provide analyzable data. The study will continue to enroll until we have complete, analyzable data on 20 subjects, or a maximum of 30 subjects will be enrolled. We will evaluate the quality of obtained data on a rolling basis and halt study enrollment as soon as we have met our goal of 20 subjects with data for analysis.

3. Key Inclusion Criteria

- A. Healthy Subjects
 - 1. Age \geq 18 years
- 4. Key Exclusion Criteria

A. Healthy Subjects

- 1. Pregnant women are excluded
- 2. Prisoners are excluded
- 3. Prior history of vascular risk factors (hypertension, diabetes, hyperlipidemia, coronary artery disease, atrial fibrillation, prior myocardial infarct or stroke, transient ischemic attack, or history of smoking)
- 4. Prior neurosurgical procedure or traumatic brain injury, including hemicraniectomy or other skull defect.

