After obtaining informed consent, all subjects will be placed supine with the head of bed flat. A non-invasive Finapres blood pressure probe will be placed on a finger to continuously record arterial blood pressure. Heart rate will be calculated by analyzing the frequency of pulsatile blood flow. After the patient is comfortable optical probes will be attached to the patient's forehead. The probes are embedded in foam pads that will be secured to each side of the forehead using a combination of medical adhesive tape and a padded Velcro strap. The pads will be placed at the temporal margin of the forehead, superior to the frontal sinuses. A transcranial Doppler ultrasound probe will be placed on the scalp at the temporal bone to insonate the middle cerebral artery (MCA) and/or the anterior cerebral artery (ACA) bilaterally and secured in place using a commercial head frame The goal will be to insonate the MCA on one side and the ACA in the contralateral side. Due to limitations of TCD insonation and variability in temporal bone windows, this may not be possible in all subjects. In this way, optical blood flow from the right and left frontal cortex and blood flow velocity in the anterior cerebral circulation will be recorded simultaneously during the study session. A large blood pressure cuff will be placed around each thigh. Both cuffs will be connected together with a large bore Y-adapter that is connected to a bulb inflator.

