Once the patient is comfortable, optical blood flow and TCD blood flow velocity will be measured for 5 minutes to establish a baseline. Both thigh cuffs will then be inflated to 20 mmHg above the patient's systolic blood pressure so that blood flow to the legs is occluded. Occlusion will be maintained for 4 minutes, followed by simultaneous deflation of bilateral cuffs and concurrent recording of blood pressure and CBF for an additional 4 minutes; 3 measures will be obtained per subject and averaged to establish a curve. The rapid deflation of the thigh cuffs will induce a 5-10% step decrease in blood pressure that is expected to last for about 10 seconds before cardiovascular reflexes restore MAP to baseline levels. During the thigh cuff deflation, changes in pulsatile blood pressure, and TCD blood flow velocity will be continuously recorded; oCBF will be recorded every 0.5 seconds. Intact autoregulation should cause a restoration of cerebral blood flow to pre-deflation values within 5-10 seconds in spite of the prolonged decrease in systemic blood pressure. We expect to see a sudden drop in optical cerebral blood flow and MCA velocity followed by a quick increase in both of these parameters. The change in cerebrovascular resistance (Δ CVR) can be calculated by dividing arterial blood pressure by cerebral blood flow. Δ CVR will be calculated using both optical CBF values and MCA velocity. The magnitude of Δ CVR over time gives a measure of dynamic cerebral autoregulation (see below for details regarding analysis). The thigh cuff occlusion will be repeated 4 times in each subject to establish a curve. A diagram of the study flow is shown below:

2. Data Collected

Information will be collected and stored securely from all study subjects. This information will include the following: age, sex, past medical history, current medications, non-prescription drug use.

3. Quantitative and Statistical Analysis

dCA will be calculated as change in blood pressure from baseline (Δ BP) divided by change in cerebral blood flow from baseline (Δ CBF) at each time point, thus dCA = Δ BP/ Δ CBF(Aaslid, Lindegaard et al. 1989); this data will be plotted against time in seconds.

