The data recorded from the TCD monitoring will be used to quantify the relation between changes in cerebrovascular resistance (Δ CVR) and blood pressure (Δ BP) as calculated by ROR = (Δ CVR/ Δ T)/ Δ BP and will be plotted along a curve for the first few seconds after cuff deflation (Aaslid, Lindegaard et al. 1989, Tiecks, Lam et al. 1995, Panerai, White et al. 1998, Lang, Mehdorn et al. 2002). The purpose of collecting TCD data is to show a correlation between the ROR calculated from TCD measures to that of dCA via DCS measurement, further validating our DCS measurements.

The optical CBF output is directly recorded as relative CBF. For blood flow velocity measured by TCD, relative CBF can be approximated by normalizing flow to baseline. This is an approximation of CBF that assumes that the vessel diameter does not change over time. Once the relative change in CVR over time is calculated, a dynamic rate of regulation index (dRoR) can be calculated by dividing the slope of the CVR over time curve by the maximum change in blood pressure (i.e. (Δ CVR/ Δ t)/ Δ BP). Intuitively, if autoregulation is intact, there should be a steep decrease in cerebrovascular resistance with a drop in blood pressure. Perfect autoregulation would result in dRoR = 1.

Baseline heart rate, MAP, and MCA velocity will be recorded for each subject and descriptive statistics including mean and standard deviation will be reported for these values. For dRoR calculation, a mean dRoR will be calculated for each subject (from 5 trials) using both optical CBF and TCD. The optical dRoR and TCD dRoR will be compared for each subject and significant differences will be evaluated using Student's t-test or Wilcoxon rank-sum as appropriate. We will quantify the correlation between dRoR measured with TCD and DCS using Pearson or Spearman correlation coefficient as appropriate.

4. Confidentiality

How will confidentiality of data be maintained? Check all that apply.

- Paper-based records will be kept in a secure location and only be accessible to personnel involved in the study.
- Computer-based files will only be made available to personnel involved in the study through the use of access privileges and passwords.
- Prior to access to any study-related information, personnel will be required to sign statements agreeing to protect the security and confidentiality of identifiable information.
- Whenever feasible, identifiers will be removed from study-related information.

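### The optical and TCD dRoR values are matched pairs, but the plan names the Wilcoxon rank-sum test, which is for independent samples, and does not say the t-test is paired

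*Combined protocol and SAP*

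**What the plan says.** Under Study Procedures, section 1 (Procedures), optical flow and "blood flow velocity in the anterior cerebral circulation will be recorded simultaneously during the study session". The same section says that "CVR will be calculated using both optical CBF values and MCA velocity", so both devices are read on the same cuff deflations.

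Section 3 (Quantitative and Statistical Analysis) then reduces the data to two numbers per subject: "a mean dRoR will be calculated for each subject (from 5 trials) using both optical CBF and TCD". For the comparison of devices, the optical and "TCD dRoR will be compared for each subject and significant differences will be evaluated using Student's t-test or Wilcoxon rank-sum as appropriate". The next sentence reads: "We will quantify the correlation between dRoR measured with TCD and DCS using Pearson or Spearman correlation coefficient as appropriate".

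The sample size, under Characteristics of the Study Population, section 2 (Accrual), rests on the correlation only: "20 subjects provides 90% power to detect a moderate correlation (rho=0.6), with alpha=0.05", one-sided. No section names the signed-rank test or describes the t-test as paired.

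**The concern.** The two dRoR values from one subject come from the same person and the same deflations. They are matched pairs, and the correlation analysis already treats them so. The rank-sum test assumes two independent groups; its counterpart for pairs is the signed-rank test. The phrase leaving the choice to what is appropriate reads as a choice between a parametric and a non-parametric test, and no distribution of the data makes rank-sum suitable for pairs.

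The study aims to validate the optical device against TCD. Pearson and Spearman coefficients do not change if one device reads higher by a constant, so the difference test is the only planned analysis that could reveal such an offset. An offset matters because the plan gives dRoR an absolute scale, with 1 standing for perfect autoregulation. Ignoring positive pairing pushes the result towards no significant difference, and does so more strongly the better the devices correlate. The plan expects them to correlate tightly.

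**Working it through.** **Inputs from the documents.** 20 analysable subjects; one mean dRoR per subject per device; rho = 0.6 and one-sided alpha = 0.05 for the correlation test.

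**Assumptions, because the documents give no figure.** Bivariate normal dRoR, equal between-subject SDs for the two devices, two-sided 5% for the difference test, and offsets of 0.5 to 1.0 SD. The value rho = 0.6 is only the sizing assumption, so a range is shown.

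**1. The plan's own figure.** By Fisher's z, with atanh(0.6) = 0.693:

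- n = ((1.645 + 1.282) / 0.693)² + 3 = 20.8
- Power at n = 20: Φ(0.693 × √17 − 1.645) = 88.7%. Simulating the exact test gives 90.3%.

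The stated 90% reproduces. It concerns the correlation and does not depend on the choice of difference test.

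**2. Standard error of the device difference.** With common SD σ, the paired variance of the mean difference is 2σ²(1 − rho)/n; the unpaired formula uses 2σ²/n. The ratio of standard errors is 1/√(1 − rho):

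- rho = 0.6: 1/√0.4 = 1.58
- rho = 0.9: 1/√0.1 = 3.16

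**3. 95% CI half-width at rho = 0.6, in SD units.**

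- Unpaired: t(0.975; 38) × √(2/20) = 0.640
- Paired: t(0.975; 19) × √(0.8/20) = 0.419

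**4. Rejection rates by simulation, n = 20 pairs** (100,000 datasets per cell for the t-tests, 20,000 for the rank tests):

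| rho | True offset (SD) | Unpaired t | Paired t | Rank-sum | Signed-rank |
|---|---|---|---|---|---|
| 0 | 0.5 | 33.8% | 32.4% | 31.9% | 30.6% |
| 0.3 | 0 | 2.1% | 5.1% | 2.1% | 4.6% |
| 0.3 | 0.5 | 31.1% | 43.3% | 29.3% | 41.3% |
| 0.6 | 0 | 0.3% | 4.9% | 0.5% | 5.1% |
| 0.6 | 0.5 | 27.2% | 66.0% | 25.6% | 63.7% |
| 0.6 | 0.75 | 70.4% | 94.5% | 66.6% | 93.1% |
| 0.6 | 1.0 | 95.3% | 99.7% | 93.6% | 99.6% |
| 0.9 | 0.5 | 17.1% | 99.7% | 19.7% | 99.6% |

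Separate runs put the rank-sum rejection rate with no offset at rho = 0.6 between 0.3% and 0.5%. The spread does not affect the conclusion.

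**5. Offset detectable with 80% power, unpaired against paired t.**

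- rho = 0.3: 0.87 against 0.78 SD
- rho = 0.6: 0.82 against 0.59 SD
- rho = 0.9: 0.75 against 0.30 SD

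**6. Unequal SDs.** The general ratio of standard errors is √[(s₁² + s₂²)/(s₁² + s₂² − 2·rho·s₁·s₂)]. With one SD twice the other (assumed):

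- rho = 0.6: √(5/2.6) = 1.39
- rho = 0.9: √(5/1.4) = 1.89

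At rho = 0.6 and an offset of 0.5 root-mean-square SD, power is then 29% unpaired against 55% paired.

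**The case against.** The strongest reply is that this is a slip of wording. The sentence speaks of comparing the two values within each subject, the next sentence correlates the same pairs, and Student's t-test is a family name that includes the paired form. On that reading only the non-parametric fallback is wrong, and the t-test figures above describe an analysis the plan may never run. This is fair as to the t-test, where the fault is an omission. It does not rescue the rank-sum test, and the rank-test columns show nearly the same loss.

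Second, the difference test is not the primary analysis. It has no stated level, sidedness or decision rule, and the sample size does not rest on it. With positive correlation, ignoring the pairing makes the test conservative, so it does not create false claims that the devices differ. All of that stands. The harm is a missed offset, and it is realised when a non-significant result is taken as agreement. The plan does not say it will read the result that way, but it does not rule it out.

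Third, the size depends on equal SDs. The devices measure different quantities, frontal tissue flow and large-artery velocity, so their SDs may differ. Step 6 shows the loss shrinks but remains substantial.

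Fourth, substituting signed-rank and adding the word paired would cure the defect; an interval and limits of agreement go further. That is also true. They come from the same differences at no extra cost.

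**Conclusion.** The concern holds. The rank-sum test is wrong for these data as written, and the form of the t-test is left open. At rho = 0.6 with equal SDs, an analyst who ignored the pairing would have about a one in four chance of detecting a 0.5 SD offset, against about two in three with a paired test. The loss is modest at rho = 0.3, nil at rho = 0 and severe at rho = 0.9; offsets near 1 SD would usually be found either way. These sizes rest on normality, a two-sided 5% level and assumed offsets, since the documents give no dRoR SD or expected bias. The correlation analysis and the target of 20 subjects stand. The point should be fixed because it weakens the plan's only check for a constant offset between the devices.

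**What to change.** Replace the sentence on testing the device difference with wording such as:

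> The within-subject difference (optical minus TCD dRoR) will be tested with a paired t-test, or with the Wilcoxon signed-rank test if the differences are clearly non-normal. It will be reported as the mean difference with its 95% confidence interval and 95% limits of agreement. A non-significant difference will not by itself be taken as agreement.

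The essential part is naming the two paired tests; the rest reports the same differences more fully. The cost is one sentence in the analysis section, with no new data, subjects or procedures. If paired tests were intended all along, the change only makes the plan say so.

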Non-Invasive Measurement of Dynamic Autoregulation of Cerebral Blood Flow Using Diffuse Correlation Spectroscopy

Principal Investigator:	[name], MSCE [name] [contact]
	[contact]
IRB Number:	821705
NCT number:	NCT02442856
Date:	March 17, 2016

Application for Review of Human Research: IRB Protocol Summary Biomedical Research

Section II

Principal Investigator: [name], MSCE [name] [contact]

PROTOCOL # 821705

Date: March 17, 2016

PROTOCOL TITLE

1. *Full Title:* Non-Invasive Measurement of Dynamic Autoregulation of Cerebral Blood Flow Using Diffuse Correlation Spectroscopy

2. Brief Title: Non-invasive Measurement of Cerebral Dynamic Autoregulation

STUDY SPONSORSHIP

1. Funding Sponsor: NIH R25 Research Grant

PROTOCOL ABSTRACT

List of Abbreviations

OBJECTIVES

1. Overall Objectives

The overall objective of this study is to evaluate the use of diffuse correlation spectroscopy (DCS) to non-invasively measure dynamic cerebral autoregulation (dCA). Cerebral autoregulation (CA) refers to the process by which cerebral blood vessels change their caliber to ensure constant cerebral blood flow (CBF) in the face of changes in cerebral perfusion pressure (CPP). Optical cerebral blood flow (oCBF) measurements will be correlated with changes in arterial blood pressure (ABP) to assess how CBF is maintained in response to changes in ABP. CA measured by DCS will be compared with reference measurements using Transcranial Doppler (TCD).

2. Primary Objective

The primary objective of this study is to validate the use of DCS to quantify dCA in healthy controls. We will measure dCA with both TCD and DCS during acute changes in mean arterial pressure using thigh cuff deflation techniques in healthy subjects. Measurements will be compared between TCD and DCS in order to validate DCS as a tool to measure dCA. We hypothesize that DCS based measurements will be tightly correlated to TCD based measurements. We hypothesize that continuous oCBF measurements will allow calculation of an autoregulation index that will correlate well with established methods for measuring CA using TCD. The primary measured variable will be relative change in cerebral blood flow using DCS.

BACKGROUND

Cerebral Autoregulation

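### Optical and TCD dRoR are built from the same finger blood pressure trace, so part of their correlation can be shared input; a flow-only correlation beside it would be a cheap safeguard

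*Combined protocol and SAP*

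**What the plan says.** Four parts of the protocol bear on this.

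- **Objectives, 2. Primary Objective.** The aim is to validate DCS against TCD for dynamic autoregulation. "We hypothesize that DCS based measurements will be tightly correlated to TCD based measurements". The section also states: "The primary measured variable will be relative change in cerebral blood flow using DCS".
- **Accrual.** "20 subjects provides 90% power to detect a moderate correlation (rho=0.6), with alpha=0.05, based on a single sided test of correlation". The null value is not written; I take it as rho=0.
- **Study Procedures, 1. Procedures.** There is one pressure source: "A non-invasive Finapres blood pressure probe will be placed on a finger to continuously record arterial blood pressure". The change in cerebrovascular resistance (CVR) "can be calculated by dividing arterial blood pressure by cerebral blood flow", and this is done for both devices: "CVR will be calculated using both optical CBF values and MCA velocity". The pressure step after cuff release is 5-10% and is "expected to last for about 10 seconds before cardiovascular reflexes restore MAP to baseline levels".
- **Study Procedures, 3. Quantitative and Statistical Analysis.** dRoR is the slope of CVR over time divided by the maximum pressure change. It is averaged per subject for each device, compared by t-test or rank-sum, and correlated: "We will quantify the correlation between dRoR measured with TCD and DCS using Pearson or Spearman correlation coefficient as appropriate". The same section says that DCS output is already relative flow and that TCD velocity can be normalised to baseline. It uses both only to build CVR.

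**The concern.** The pressure trace enters the numerator and the denominator of both indices being correlated. Anything peculiar to a subject's pressure recording, whether measurement error or early recovery of pressure, moves the two indices together. A positive correlation could then come from the flow signals agreeing, from the common pressure input, or from both, and the correlation alone cannot tell these apart.

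This matters because the study exists to show that the optical flow signal tracks the reference. Nothing in the analysis section fills the gap. The t-test or rank-sum comparison also uses dRoR, and no analysis sets optical flow against TCD flow, although the primary measured variable is itself a flow quantity that contains no pressure.

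**Working it through.** **1. The plan's own figure.** With n=20, rho=0.6 and one-sided alpha 0.05, Fisher's z gives power = Φ(atanh(0.6)·√17 − 1.645) = Φ(0.693 × 4.123 − 1.645) = Φ(1.213) = 88.7%. With the bias term rho/(2(n−1)) = 0.0158 added to atanh(0.6), it is 89.9%. Simulation of the exact test gives 90.4%. The stated 90% is reproduced.

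**2. Critical value.** With t(0.95; 18 df) = 1.734, r = 1.734/√(18 + 1.734²) = 0.378. This is the pass mark used below.

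**3. Where pressure enters.** Write pressure p and flow f as fractions of baseline. For small changes the slope of CVR = p/f is about b_p − b_f, where b_p and b_f are the slopes of pressure and flow. With D the maximum pressure change,

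- dRoR(DCS) ≈ (b_p − b_DCS)/D
- dRoR(TCD) ≈ (b_p − b_TCD)/D

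Both contain b_p and D. If pressure is error-free and held, b_p = 0. If flow falls with pressure and then recovers, b_f is proportional to D, so D cancels and only recovery speed is left. In that case there is no artefact. Error in p, or pressure recovery inside the window, makes b_p non-zero in both indices. An error in D rescales both.

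**4. Rough size, by hand.** Assume independent error per 0.5 s sample, with SD a for pressure, o for optical flow and c for TCD. Window length and number of trials scale all three slope variances equally and cancel. If DCS carries no subject-level information on recovery speed, then

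rho(artefact) ≈ a²/√[(a²+o²)(a²+c²)]

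and P(r>0.378) ≈ 1 − Φ[(atanh 0.378 − atanh rho)·√17]. This ignores true spread in TCD recovery, which lowers rho, and error in D.

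**5. Simulation.** Assumed: n=20; a 5-10% step held beyond the slope window (6-14 s); flow recovery time constant 1.5-4 s between subjects; an uninformative DCS with a common 2.5 s constant; slope window 0-3 s or 1-3.5 s. Percentages are the share of studies with r>0.378.

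| Optical / TCD noise | Pressure error | rho by hand | By hand | Simulated |
|---|---|---|---|---|
| 2% / 1% | 0 | 0 | 5% | about 6% |
| 2% / 1% | 1% | 1/√(5×2) = 0.316 | 38% | 35-42% |
| 2% / 1% | 2% | 4/√(8×5) = 0.632 | 92% | 89-94% |
| 5% / 3% | 1% | 1/√(26×10) = 0.062 | 8% | 9-11% |
| 5% / 3% | 2% | 4/√(29×13) = 0.206 | 22% | 24-25% |

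The error need not be independent between samples. Over a wider grid (optical noise 1-5%, TCD noise 1-3%), 1% error with lag-1 autocorrelation 0.9 gave 8-65%. A subject-level error of SD 10% in the size of the drop, with no sample error, gave 7-58%.

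**6. The flow-only alternative.** The measure is the fraction of the initial flow drop (0-0.5 s) recovered by 3.5-5 s, with pressure still held. At 2%/1% noise the uninformative DCS passes in 4-6% of studies, and a perfectly tracking DCS in 89-99%. At 5%/3% the perfectly tracking DCS passes in only about 22-25%.

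**7. Precision at n=20.** The 95% limits are tanh(atanh r ± 1.96/√17).

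- r=0.378: −0.08 to 0.70
- r=0.6: 0.21 to 0.82
- r=0.8: 0.55 to 0.92

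The lower limit reaches 0.6 at tanh(0.693 + 0.475) = 0.824.

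**The case against.** The strongest reply is that under the plan's stated conditions there is no artefact. The protocol expects the pressure step to last about 10 seconds and looks at the first few seconds after deflation. Every inflated rate above needs a pressure error or early recovery that the documents do not quantify, and the rates fall sharply when flow noise is high. This stands. The figures show what is possible and do not estimate a bias in this study.

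Second, autoregulation relates flow to pressure, so a flow-only measure answers a narrower question. That also stands, and it is why the measure belongs beside dRoR and should not replace it.

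Third, the flow-only measure has a common input of its own if pressure recovers inside its window. An uninformative DCS then passes in 11-91% of studies when pressure ramps back from time zero, and in 68-98% when it is restored abruptly within the window in some subjects. Adjusting for the fraction of the pressure drop recovered brings these to 5-7% and 5-12% with error-free pressure, but only to 6-18% and 10-50% with 1% error. Hence the early window and the caveat in the fix.

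A reader might also infer that the plan will treat a just-significant r of 0.378 as validation. It does not say so. The analysis section speaks of quantifying the correlation, and the accrual section only sizes a test. Reporting confidence intervals is ordinary good practice, not the correction of an error.

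**Conclusion.** The point holds as a low-severity improvement. The shared trace and the absence of a flow-to-flow comparison follow directly from the protocol. The size of any built-in correlation does not: it runs from nil with error-free, held pressure to 89-94% false passes at an assumed 2% pressure error with low flow noise, and back to 24-25% at the same error with high flow noise.

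Three stronger readings are tempting, and the documents support none of them.

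- **That a positive dRoR correlation would be an artefact, or that the design is invalid.** The mechanism is possible, but nothing in the documents shows that it operates to a material degree.
- **That the correlation could arise if DCS carried no subject-level information at all.** The simulated optical flow still follows each subject's pressure drop. What it lacks is subject-level information on the speed of recovery, and the finding is limited to that.
- **That the other planned correlation fails too.** The analysis section gives, as the purpose of the TCD data, correlating TCD ROR with a DCS dCA ratio. That comparison was not assessed here.

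The sample-size figure is not disputed.

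**What to change.** In Study Procedures, 3. Quantitative and Statistical Analysis:

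1. Keep the dRoR correlation and state that the two indices share one pressure trace.
2. Beside it, report a flow-only correlation between DCS relative CBF and normalised TCD velocity. Use the fraction of the initial drop recovered in an early window, fixed in advance and chosen to end well before the expected restoration of pressure at about 10 seconds.
3. Report each subject's pressure restoration time. Where pressure recovers inside the window, also give the partial correlation adjusted for the fraction of the pressure drop recovered in that window, and say that this reduces the problem but may not remove it.
4. Give every r with its 95% CI. For orientation, at n=20 the lower limit reaches 0.6, the value that the accrual section calls moderate, only at an observed r of about 0.82 or more.

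The cost is one window to fix in advance and a little more analysis of data already recorded, with no new subjects or procedures. The flow-only result may be inconclusive if optical noise is high, and it could lead to a less favourable conclusion about DCS.

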Prior human studies have documented that CA tightly controls flow over a range of mean arterial pressure from 60-150mmHg (Paulson, Strandgaard et al. 1990). However, recent studies suggest that autoregulation may be impaired for up to 2 weeks following acute ischemic stroke (AIS), and that CA impairment may lead to poorer outcomes (Dawson, Blake et al. 2000, Dawson, Panerai et al. 2003, Reinhard, Roth et al. 2005, Atkins, Brodie et al. 2010, Aoi, Hu et al. 2012, Reinhard, Rutsch et al. 2012). The extent of CA impairment in acute stroke is likely highly variable. Early human studies determined that CA is impacted by age-related diseases, including hypertension and diabetes (McHenry, West et al. 1974, Dawson, Blake et al. 2000, Aries, Elting et al. 2010). Animal models have also demonstrated impaired dCA in AIS and that the tissue becomes much more vulnerable to changes in blood pressure (Yang, Shah et al. , Smeda, VanVliet et al. 1999, Smeda 2003). Based on the principle that CA is impaired following an acute ischemic event, current treatment recommendations revolve around tactics that increase cerebral perfusion (Goldstein 2000, Dawson, Panerai et al. 2003). The American Heart Association/American Stroke Association guidelines recommend permissive hypertension to systolic of 220mmHg and diastolic to 120mmHg (Adams, del Zoppo et al. 2007). However, above the upper limit of CA blood vessels are

not able to adequately constrict to limit blood flow, which can lead to endothelial injury, breakdown of the bloodbrain barrier, and potentially cerebral edema (Nazir, Overell et al. 2004, Nazir, Overell et al. 2005). Data derived from this project will provide the groundwork for future projects using the DCS technique which may be able to establish a new bedside mechanism for identifying patients in whom dCA is impaired, allowing for more individualized use of permissive hypertension, intravenous fluids, and vasopressors.

Limitations of existing autoregulation measurements

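### DCS is judged against TCD by a between-subject correlation of mean dRoR in healthy adults, but no spread, repeatability or agreement output is planned to show what a low or high r means

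*Combined protocol and SAP*

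**What the plan says.** Under Primary Objective the combined protocol and SAP states: "The primary objective of this study is to validate the use of DCS to quantify dCA in healthy controls". The working hypothesis is: "We hypothesize that DCS based measurements will be tightly correlated to TCD based measurements".

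The target population is "Healthy adult volunteers with no history of prior brain ischemia". Key Exclusion Criteria then remove anyone with "Prior history of vascular risk factors (hypertension, diabetes, hyperlipidemia, coronary artery disease, atrial fibrillation, prior myocardial infarct or stroke", and also TIA and smoking, as well as "Prior neurosurgical procedure or traumatic brain injury, including hemicraniectomy or other skull defect". The Background (Cerebral Autoregulation) says of some of these conditions: "Early human studies determined that CA is impacted by age-related diseases, including hypertension and diabetes".

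Under Procedures, the only stimulus is release of the thigh cuffs with the subject supine. Both devices and the finger blood pressure are recorded at the same time.

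Under Quantitative and Statistical Analysis, a mean dRoR is formed per subject for each device. The two are compared by a t-test or rank-sum test, and then: "We will quantify the correlation between dRoR measured with TCD and DCS using Pearson or Spearman correlation coefficient as appropriate". Means and SDs are promised for baseline heart rate, MAP and MCA velocity, but not for dRoR. No within-subject SD, ICC, limits of agreement or release-level model is mentioned.

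**The concern.** A correlation across subjects measures tracking relative to the spread among those subjects. If they differ little in true dRoR, or single releases are noisy, r falls even when both devices respond to the same physiology. Eligibility removes conditions that the Background itself links to altered autoregulation, and nothing in the procedure is designed to vary autoregulation within a subject. Restricted spread is therefore a reasonable expectation, though not an established fact.

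As planned, the reader would see r and a p-value for a difference in level. A low r would leave poor tracking and small spread indistinguishable. A high r could be partly produced by the common blood pressure signal, which enters both the resistance and the denominator of each index. The location test does not help, because failing to find a mean difference is not evidence that the devices agree subject by subject. What is at stake is whether the primary objective gets an interpretable answer.

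**Working it through.** **1. The plan's own figure.** Accrual gives 20 subjects, 90% power, rho = 0.6, one-sided alpha 0.05. By Fisher z, N = ((1.645 + 1.282)/atanh 0.6)² + 3 = (2.926/0.693)² + 3 = 20.8. Power at N = 20 is 88.7% by simple Fisher z, 90.0% with bias correction and the t critical value, and 90.4% by simulation. The figure reproduces, so the arithmetic is not at issue. The 0.6 must, however, be the correlation of the two averaged, error-containing indices, and Accrual states no assumption on spread or error.

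**2. Expected r under perfect tracking.** The documents give no ICC. Assume a single-release ICC equal in both devices and errors independent between devices. The reliability of a k-release mean is R = k·ICC/(1 + (k − 1)·ICC). Expected r = true rho × √(R_DCS × R_TCD), which equals R when true rho = 1. Example: ICC 0.2, k = 3 gives 0.6/1.4 = 0.43. The document gives 3 and 4 repeats under Procedures and 5 under the analysis, so all three are shown. Power is at N = 20, one-sided 0.05, by Fisher z.

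| ICC | r: k = 3 / 4 / 5 | Power: k = 3 / 4 / 5 |
|---|---|---|
| 0.1 | 0.25 / 0.31 / 0.36 | 28% / 37% / 46% |
| 0.2 | 0.43 / 0.50 / 0.56 | 60% / 73% / 83% |
| 0.3 | 0.56 / 0.63 / 0.68 | 84% / 92% / 96% |
| 0.5 | 0.75 / 0.80 / 0.83 | at least 99% |

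**3. Effect of spread alone.** Fix the error at a level that gives R = 0.90 in a widely spread population, and shrink the true between-subject SD by a factor u: R = 0.9u²/(0.9u² + 0.1). For u = 1/2, R = 0.225/0.325 = 0.69. For u = 1/3, R = 0.1/0.2 = 0.50. For u = 1/4, R = 0.056/0.156 = 0.36. The devices are unchanged throughout; only the sample differs.

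**4. Two explanations, one output.** An r of 0.40 arises from perfect tracking with R = 0.40 (single-release ICC 0.18 for k = 3, 0.12 for k = 5). It also arises from true rho 0.42 with R = 0.95, since 0.42 × 0.95 = 0.40. The planned analysis cannot separate them. With release-level values, 20 subjects and k = 3, the 95% interval for R would be about −0.25 to 0.74 in the first case and 0.90 to 0.98 in the second.

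**5. Shared error.** Let s be the fraction of release-level error variance common to both devices (assumed). Under perfect tracking, r = R + s(1 − R). For ICC 0.2, k = 3: 0.43 at s = 0, 0.57 at s = 0.25, 0.71 at s = 0.5. For ICC 0.3, k = 3: 0.56, 0.67 and 0.78. The values in step 2 are therefore not upper bounds in this design.

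**The case against.** The strongest reply is that severe attenuation is assumed. At ICC 0.3 power is still 84–96%, at 0.5 or above the loss is small, and shared blood pressure error pushes r upwards. That stands: the documents cannot show which ICC applies. It is also the reason to estimate it.

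A reader might infer four stronger things that the documents do not support.
- *That eligibility admits only people with intact autoregulation, so true dRoR hardly varies.* Autoregulation is not tested at entry, age is 18 or over with no upper limit, and volunteers from outside the university may take part. The Background says disease alters autoregulation, not that healthy people are alike.
- *That the repeat releases are thrown away.* They are recorded and averaged, and averaging raises reliability. The gap is that their variability is not a planned output.
- *That the plan would read a low r as failure of DCS.* It states no threshold and no rule for reading r.
- *That √(R_DCS × R_TCD) is a hard limit on r.* It requires independent errors, which is doubtful when both indices use one simultaneous pressure trace.

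It can also be said that the objective is already confined to healthy controls, so a scope statement adds little, and that 20 subjects give imprecise reliabilities: at ICC 0.5 the 95% interval is 0.23–0.74 for k = 3 and 0.30–0.71 for k = 5. Both points are fair. Intermediate cases may stay unresolved, but a wide interval says so openly, whereas r alone does not.

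**Conclusion.** The point holds as a gap in the planned analysis, not as a flaw in eligibility, in averaging or in the sample size calculation. The validation result rests on a statistic whose size depends on between-subject spread and release error, and the plan reports neither for dRoR. It includes no measure of agreement, although dRoR is computed on the same relative scale for both devices.

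How much this matters depends on an ICC that the documents do not give. Under equal ICCs and independent errors it is serious at about 0.2 or below (expected r at most 0.56 with perfect tracking, power 83% or less), moderate at 0.3 and small from 0.5 upwards. Shared error would raise r, which makes a high value harder to read as well. The change should be made because it costs almost nothing and makes either result interpretable.

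**What to change.** Amend Quantitative and Statistical Analysis only; eligibility, procedures and N stay as they are. Keep the subject-mean correlation and add:

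- (a) as the agreement result, the mean DCS–TCD difference in dRoR with 95% limits of agreement that allow for repeated releases;
- (b) from a random-effects model on release-level dRoR, the between- and within-subject SD and the ICC for each device, with 95% confidence intervals. A bivariate model is preferable, so that errors within a release may correlate between devices;
- (c) a statement made in advance that a low r together with low TCD reliability is inconclusive, and that conclusions apply to healthy adults.

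If √(R_DCS × R_TCD) is shown beside r, with R the reliability of the subject mean, label it as valid only under independent errors. The 3, 4 and 5 releases stated under Procedures and under the analysis must be reconciled, because the reliability of the mean depends on that number.

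The cost is some wording and a small amount of analysis of data already recorded. The drawback is wide intervals with 20 subjects.
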